7.1 DEFINITIONS

The definitions of the EU Directive 2001/20/EC Article 2 based on the principles of GCP, which is in line ICH E2A apply to this trial protocol. These definitions are given in **Table 1**.

Table 1 Definitions

Term	DEFINITION	
Adverse Event (AE)	Any untoward medical occurrence in a patient or clinical trial subject to whom a medicinal product has been administered including occurrences that are not necessarily caused by or related to that product.	
Adverse Reaction (AR)	Any untoward and unintended response to an investigational medicinal product related to any dose administered.	
Unexpected Adverse Reaction (UAR)	An adverse reaction, the nature or severity of which is not consistent with the information about the medicinal product in question set out in the Summary of Product Characteristics (SmPC) or Investigator Brochure for that product.	
Serious Adverse Event (SAE) or Serious Adverse Reaction (SAR) or Suspected Unexpected Serious Adverse Reaction (SUSAR)	 Respectively any adverse event, adverse reaction or unexpected adverse reaction that: Results in death Is life-threatening* Requires hospitalisation or prolongation of existing hospitalisation** Results in persistent or significant disability or incapacity Consists of a congenital anomaly or birth defect Is another important medical condition*** 	

- *The term life-threatening in the definition of a serious event refers to an event in which the patient is at risk of death at the time of the event; it does not refer to an event that hypothetically might cause death if it were more severe, for example, a silent myocardial infarction.
- **Hospitalisation is defined as an inpatient admission, regardless of length of stay, even if the hospitalisation is a precautionary measure for continued observation. Hospitalisations for a pre-existing condition, that has not worsened or for an elective procedure do not constitute an SAE.
- *** Medical judgement should be exercised in deciding whether an AE or AR is serious in other situations. The following should also be considered serious: important AEs or ARs that are not immediately life-threatening or do not result in death or hospitalisation but may jeopardise the subject or may require intervention to prevent one of the other outcomes listed in the definition above; for example, a secondary malignancy, an allergic bronchospasm requiring intensive emergency treatment, seizures or blood dyscrasias that do not result in hospitalisation or development of drug dependency.

7.1.1 PRODUCT

The trial is testing chlorhexidine and emollient for topical use.

7.1.2 ADVERSE EVENTS

Adverse Events include:

- An exacerbation of a pre-existing illness
- An increase in frequency or intensity of a pre-existing episodic event or condition
- A condition (even though it may have been present prior to the start of the trial) detected after trial product administration
- Continuous persistent disease or a symptom present at baseline that worsens following administration of the trial treatment

Assessment of adverse events (AEs) is challenging in neonates since standard grading scales do not apply; for example, normal ranges of laboratory parameters vary enormously with age and normal function is difficult to specify.

Adverse events will therefore be assessed using an adapted version of the DAIDS scale for neonates, that has been used in previous neonatal trials by groups such as IMPAACT,³⁸ including studies conducted for regulatory FDA approval (Appendix II).

Each adverse event will be assessed at each scheduled visit and graded by the investigator according to the Adapted DAIDS score for neonates, reproduced from the IMPAACT network³⁸ (Appendix II).

Skin damage and hypothermia will both be separately assessed as part of primary and secondary outcomes and graded according to the classification shown in **Appendix I** and **Section 6.3**.

7.1.3 SAFETY MANAGEMENT

In the case of adverse events, standard operating procedures will be available for anticipated events including hypothermia, skin damage, as well as rare and highly unlikely accidents such as splash injury to the eye from chlorhexidine.

7.1.4 EXEMPTED ADVERSE EVENTS

Adverse Events do not include:

- Medical or surgical procedures; the condition that leads to the procedure is the adverse event
- Pre-existing disease or a condition present before treatment that does not worsen
- Hospitalisations where no untoward or unintended response has occurred, eg, social admissions
- Overdose of medication without signs or symptoms

7.2 INVESTIGATOR RESPONSIBILITIES

Presence of non-serious AEs in **Appendix II** will be documented in CRFs/worksheets at each scheduled visit.

All AEs meeting the seriousness criteria defined in **Table 2**, including but not limited to those related to skin damage, hypothermia or neurological disturbance should be notified to CTU using the SAE Form within 24 hours of the investigator becoming aware of the event.

7.3 INVESTIGATOR ASSESSMENT

7.3.1 SERIOUSNESS

When an AE occurs, the investigator responsible for the care of the baby must first assess whether or not the event is serious using the definition given in **Table 2**. If the event is serious, then an SAE Form must be completed and the MRC CTU notified within 24 hours of the investigator becoming aware of the event.

7.3.2 SEVERITY OR GRADING OF ADVERSE EVENTS

AEs, serious or not serious, should be graded using the Adapted DAIDS score for neonates, reproduced from the IMPAACT network³⁸ (Appendix II).

7.3.3 CAUSALITY

The investigator must assess the causality of all serious events in relation to the trial treatment using the definitions in **Table 2**. There are five categories: unrelated, unlikely, possible, probable, and definitely related. If the causality assessment is unrelated or unlikely to be related, the event is classified as an SAE. If the causality is assessed as possible, probable or definitely related, then the event is classified as an SAR.

RELATIONSHIP	DESCRIPTION	SAE TYPE
Definitely	There is clear evidence to suggest a causal relationship and other possible contributing factors can be ruled out.	SAR
Probably	There is evidence to suggest a causal relationship and the influence of other factors is unlikely.	SAR
Possibly	There is some evidence to suggest a causal relationship (for example, because the event occurs within a reasonable time after administration of the trial medication). However, the influence of other factors may have contributed to the event (for example, the patient's clinical condition, other concomitant treatments).	SAR
Unlikely	There is little evidence to suggest that there is a causal relationship (for example, the event did not occur within a reasonable time after administration of the trial medication). There is another reasonable explanation for the event (for example, the patient's clinical condition, other concomitant treatment).	Unrelated SAE
Unrelated	There is no evidence of any causal relationship	Unrelated SAE

Table 2 Assigning Type of SAE Through Causality

If an SAE is considered to be related to trial treatment and chlorhexidine or emollient is stopped, refer to Sections 5.2.1.2 and 5.2.2.2 for more information on dose interruptions and discontinuations.

7.3.4 NOTIFICATION

The MRC CTU should be notified of all SAEs within 24 hours of the investigator becoming aware of the event. Investigators should notify the MRC CTU of all SAEs occurring from the time of signature of the informed consent form until 28 days after randomisation.

7.3.5 Notification Procedure

The SAE Form must be completed by an investigator (the clinician, named on the Signature List and Delegation of Responsibilities Log, who is responsible for the baby's care; this will be either the Principal Investigator or another medically qualified person with delegated authority for SAE reporting). Due care should be paid to the grading, and assessment of causality of the event, as outlined above. In the absence of the responsible investigator, the form should be completed and signed by a member of the site trial team and emailed. The responsible investigator should subsequently check the SAE Form, make changes as appropriate, sign and then re-email to the MRC CTU as soon as possible. The initial report must be followed by detailed, written reports as appropriate.

The minimum criteria required for reporting an SAE are the trial number and date of birth, name of investigator reporting, the event, and why it is considered serious.

The SAE Form must be sent by encrypted email to the MRC CTU (see below).

Follow-up: babies must be followed up until clinical recovery is complete and laboratory results have returned to normal or baseline, or until the event has stabilised. Follow-up should continue after completion of protocol treatment if necessary. A further SAE Form, indicated as 'Follow-up SAE Form' should be completed and emailed to the MRC CTU as information becomes available (or where a small amount of fields are updated, the original SAE form may be modified following GCP). Extra, annotated information and/or copies of test results may be provided separately. The baby must be identified by trial number and date of birth. The baby's name must not be used on any correspondence and should be deleted from any test results.

Staff should follow their institution's procedure for local notification requirements.

SAE REPORTING

Within 24 hours of becoming aware of an SAE, please email a completed SAE form to the MRC CTU on [contact]

7.4 MRC CTU RESPONSIBILITIES

Medically-qualified staff at the MRC CTU and/or the Chief Investigator (or a medically-qualified delegate) will review all SAE reports received and assess expectedness as necessary. The causality assessment given by the local investigator at the hospital cannot be overruled; in the case of disagreement, both opinions will be provided in any subsequent reports.

The MRC CTU is delegated by the Sponsor for the reporting of SUSARs and other SARs to the regulatory authorities and the research ethics committees, as appropriate.

8 QUALITY ASSURANCE & CONTROL

8.1 RISK ASSESSMENT

The Quality Assurance (QA) and Quality Control (QC) considerations have been based on a formal Risk Assessment, which acknowledges the risks associated with the conduct of the trial and how to address them with QA and QC processes. QA includes all the planned and systematic actions established to ensure the trial is performed and data generated, documented and/or recorded and reported in compliance with the principles of GCP and applicable regulatory requirements. QC includes the operational techniques and activities done within the QA system to verify that the requirements for quality of the trial-related activities are fulfilled. This Risk Assessment has been reviewed by the MRC CTU's Research Governance Committee (RGC) and has led to the development of a Data Management Plan (DMP), Safety Reporting Plan and Monitoring Plan which will be separately reviewed by the Quality Management Advisory Group (QMAG).

8.2 CENTRAL MONITORING AT THE MRC CTU

Each site will be responsible for its own data entry and local trial management. Data will be entered into the online trial database directly at the site. The site will retain the original CRFs/worksheets. Data stored on the central database will be checked at the MRC CTU for missing or unusual values (range checks) and checked for consistency within neonates over time. If any problems relating to data quality are identified, the site will be contacted and asked to verify or correct the entry. Changes will be made on the original CRF/worksheet and entered into the database at the site. The MRC CTU will also send reminders for any overdue and/or missing data with the regular inconsistency reports of errors.

Other essential trial issues, events and outputs will be detailed in the Monitoring Plan that is based on the trial-specific Risk Assessment.

8.3 ON-SITE MONITORING

The frequency, type and intensity for routine monitoring and the requirements for triggered monitoring will be detailed in the Monitoring Plan. This plan will also detail the procedures for review and sign-off.

A detailed site initiation meeting with training will be performed at each trial site by staff from the MRC CTU either face to face or online. The site initiation meeting will include training in the administration and side effects of study products, as well as the trial procedures.

8.3.1 DIRECT ACCESS TO PATIENT RECORDS

Participating investigators should agree to allow trial-related monitoring, including audits, ethics committee review and regulatory inspections by providing direct access to source data and documents as required. Parental/caregiver consent for this must be obtained. Such information will be treated as strictly confidential and will in no circumstances be made publicly available.

The trial data and consent/assent should all be verifiable from source documents which may include paper notes and electronic health records.

Not all such information will be monitored; rather the monitoring plan will describe a risk-based approach to monitoring based on ongoing random samples of clinical and laboratory data, which may be increased if issues are identified.

The investigator/institution should maintain adequate and accurate source documents and trial records that include all pertinent observations on each of the site's trial subjects. Source data should be attributable, legible, contemporaneous, original, accurate, and complete. Changes to source data should be traceable, should not obscure the original entry, and should be explained if necessary (e.g., via an audit trail).

8.3.2 CONFIDENTIALITY

We plan to follow the principles of the EU General Data Protection Regulation (GDPR) as well as being compliant with national data laws in the countries where the trial is being conducted. In particular, the investigator must ensure that baby's anonymity will be maintained and that their identity is protected from unauthorised parties. Babies will be assigned a trial identification number and this will be used on CRFs/worksheets; they will not be identified by name. The investigator will keep securely a trial register showing trial identification numbers, initials and date of admission and age at admission, held only at the local site. The unique trial number (or laboratory tracking number) will identify all laboratory specimens, CRFs/worksheets, and other records and no names or initials will be used on forms or samples, in order to maintain confidentiality. Date of birth will be collected as a data item since all babies will be under 28 days old and hence is needed to calculate age precisely. All records will be kept in locked locations. Clinical information will not be released without written permission, except as necessary for monitoring by the trial monitors.

9 STATISTICAL CONSIDERATIONS

9.1 METHOD OF RANDOMISATION

Randomisation will be online with allocation concealment. The design will not be blinded as this is not practical given the factors evaluated. However, the efficacy co-primary endpoint (bacterial colonisation) will be assessed by laboratory staff blinded to randomisation.

9.2 OUTCOME MEASURES

9.2.1 CO-PRIMARY OUTCOME MEASURES

- Skin bacterial load change in colony forming units (CFUs) in the nose (1 swab), cervical skin folds and umbilicus (1 pooled swab), and peri-rectal area (1 swab) from randomisation (before chlorhexidine application) to D3+/- 1 day and D8 +/- 3 days microbiology data collection (efficacy).
- Modified neonatal skin condition score (see Appendix I) used before each application of chlorhexidine, or alternate working days in controls (safety). The primary analysis of this outcome will consider the absolute score. Secondary analysis of this outcome will consider graded toxicity (see Appendix I).

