The effect of each treatment arm will be assessed within a single model with each factor being fitted independently as a factor, and not as a continuous variable. Comparison of main effects within arms will be assessed using the estimate and 95% confidence interval of the comparison of differences between factors and in comparison, to control. As this is a pilot trial, the sample size was not powered to robustly detect interactions between chlorhexidine concentrations/frequencies and emollients and so we will not test these formally, but will use exploratory analyses to assess whether there is any evidence supporting individual interactions testing each one, one at a time. As this is a pilot trial and the two co-primary outcomes capture different aspects (efficacy and safety) there will be no adjustment for multiple testing, nor for the two different bacterial load outcomes since we expect a reduction in colonisation on the skin, but potentially no change in colonisation peri-rectally.

Similar mixed models will be used to analyse change in skin temperature after vs before each application, including individual as a random effect, the change in temperature as the outcome and the pre-application (baseline) temperature as a factor. Acquisition and loss of each species will be analysed as a binary outcome variable, compared with baseline, in the relevant population (those without the species of interest at baseline, or with the species of interest at baseline, respectively).

Presence/absence of each species at each assessment will also be compared between randomised groups using mixed models, again with individual as a random effect, and with baseline presence as a factor.

Frequency of SAEs will be tabulated by randomised group, and compared using exact logistic models (or time-to-event models if AEs occur in >10% of the trial population overall). SAEs will also be tabulated by grade. Similar analyses will be conducted for the AEs in Appendix II.

A Statistical Analysis Plan will be written and approved by the Trial Management Group (TMG) and the DMC before the first interim analysis is reviewed by the DMC.

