APPENDIX I SKIN SCORE ASSESSMENT

Skin toxicity score

Adapted from Lund & Osborne.³¹ The skin should be scored on each of the three domains (dryness, erythema and skin breakdown), and then the total score is the sum of the three components (minimum score 0, maximum score 12).

Highest grade from:

Grade 1 = Score of \geq 1 in \geq 2 categories

Grade 2 = Score of \geq 2 in \geq 2 categories

Grade 3 = Score of \geq 3 in \geq 2 categories

Grade 4 = Score of \geq 4 in \geq 2 categories

Score	Description
Domain 1	Dryness
0	Normal
1	Dry skin +/- scaling <50%
2	Dry skin + scaling >50% +/- cracking/fissures <50%
3	Very dry + cracking / fissures >50%
4	Very dry + cracking / fissures >75%
Domain 2	Erythema
0	Normal
1	Erythema <25%
2	Erythema 25-50%
3	Severe Erythema 50-75%
4	Severe Erythema >75%
Domain 3	Skin breakdown
0	Normal
1	Skin breakdown/ulceration/vesicles <5%
2	Skin breakdown/ulceration/vesicles 5-25%
3	Skin breakdown/ulceration/vesicles 25-50%
4	Skin breakdown/ulceration/vesicles >50%

Figure 3: Skin Affected Area assessment

Modified Lund and Browder chart for estimation of BSA burn involvement in infants and children. (From Harwood-Nuss A, Wolfson A, Linden C. *The clinical practice of emergency medicine*. Philadelphia: Lippincott-Raven; 1996:1207⁴⁰

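### The Appendix I skin toxicity grade equals the middle of the three domain scores, so it understates toxicity whenever breakdown is the worst domain and gives isolated breakdown no grade

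*Protocol*

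**What the plan says.** Protocol 9.2.1 makes the absolute skin score the primary analysis of the safety co-primary and adds the grade as a further analysis: "Secondary analysis of this outcome will consider graded toxicity (see Appendix I"). The trial summary lists both absolute score and grade under this outcome.

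Appendix I scores dryness, erythema and breakdown from 0 to 4 each, and "the total score is the sum of the three components (minimum score 0, maximum score 12"). The top breakdown level is "Skin breakdown/ulceration/vesicles >50" per cent. Grades 1, 2, 3 and 4 require a score of at least 1, 2, 3 and 4 respectively, each in two or more categories, and the highest grade met is taken. No route to a grade runs through a single domain.

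On which scale applies, Protocol 7.1.2 points to Appendix I for skin and to Section 6.3 for hypothermia: "Skin damage and hypothermia will both be separately assessed as part of primary and secondary outcomes and graded according to the classification shown in". Protocol 7.3.2 says more generally that "AEs, serious or not serious, should be graded using the Adapted DAIDS score for neonates", which is Appendix II. Appendix II has 20 rows and none concerns skin.

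Protocol 9.5 plans for serious events: "Frequency of SAEs will be tabulated by randomised group, and compared using exact logistic models", and "SAEs will also be tabulated by grade". It continues: "Similar analyses will be conducted for the AEs in Appendix II".

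**The concern.** A toxicity grade should rise with the severity of the damage it describes. Breakdown is the domain that records loss of skin integrity, yet under a two-domain rule it cannot set the grade by itself. The most extensive breakdown on the scale, with no dryness or redness, is treated as ungraded, while a little dryness with a little redness is graded.

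The protocol elsewhere treats one domain as clinically important. A score of 2 or more in any domain bars entry (3.2), and a score above 2 in any category prompts the clinician to consider interrupting or stopping chlorhexidine (5.2.1.2).

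Two things are at stake. Section 10.2.1 names skin damage as the main ethical concern, and the pilot is to choose the concentration, frequency and emollient for a larger trial. The stated hypothesis is also that emollient improves skin condition and so permits a more effective concentration. If emollient reduces dryness, the grade can fall for that reason alone while breakdown stays as it was.

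**Working it through.** **Inputs (Appendix I).** Three domains D (dryness), E (erythema), B (breakdown), each an integer from 0 to 4. Grade = the highest k in 1 to 4 such that at least two of D, E, B are ≥ k; no grade (written 0) if no k qualifies.

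**Reproducing the plan's own figure.** Total = D + E + B runs from 0 to 3 × 4 = 12, as Appendix I states. The number of possible patterns is 5³ = 125.

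**Step 1: what the grade is.** At least two of three scores are ≥ k exactly when the middle score is ≥ k, so grade = median(D, E, B). Enumeration confirms this in 125 of 125 patterns.

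**Step 2: grade against breakdown.** The median is below B exactly when B is greater than both D and E. For B = b there are b² such patterns (D and E each from 0 to b − 1): 1 + 4 + 9 + 16 = 30. The shortfall B − grade is 1 level in 16 patterns, 2 in 9, 3 in 4 and 4 in 1. Of the 50 patterns with B of 3 or 4, 18 grade below 3: 2 have no grade, 6 are Grade 1 and 10 are Grade 2.

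**Step 3: ordering.**

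| D | E | B | Total | Grade |
|---|---|---|---|---|
| 1 | 1 | 0 | 2 | 1 |
| 0 | 0 | 4 | 4 | none |
| 1 | 0 | 4 | 5 | 1 |

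The second row has twice the total of the first, and breakdown over more than half the skin, yet it is the one without a grade.

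**Step 4: sensitivity to dryness.** There are 4 × 5 × 4 = 80 patterns with D ≥ 1 and B ≥ 1. Lowering D by one point with E and B fixed lowers the grade in 30 of them. In 20 of those 30 the new grade is below B. Example: (2, 0, 2) is Grade 2; (1, 0, 2) is Grade 1, with breakdown still 2.

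**Step 5: is there another scale?** Section 7.1.2 sends skin damage to Appendix I. Section 7.3.2 and the adverse-event analyses in 9.5 point to Appendix II, which has no skin row. So a serious event of isolated breakdown has no defined level in the table of SAEs by grade.

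**Step 6: the amended rule.** Let grade* = max(current grade, B). It differs from the current grade in exactly the 30 patterns of Step 2. A one-point fall in dryness then lowers the grade in 10 of 80 patterns, never to below B. If the rule starts only at B ≥ 2, it changes 29 patterns, since (0, 0, 1) is left as it is.

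All counts are of possible score patterns and need no assumption. They say nothing about how often each pattern will occur in babies.

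**The case against.** The strongest reply is that little depends on the grade. The primary analysis is the absolute score, to which isolated breakdown contributes its full 1 to 4 points. Skin damage that meets a seriousness criterion is reported within 24 hours (7.2). SAEs go weekly to the DMC (9.4) and are compared by randomised group (9.5). Section 1.4.1 says skin damage has been very rare in earlier studies, so few babies may be affected. The grade also works properly when erythema or dryness is at least as high as breakdown. All of this stands and limits the consequence. It does not make the grade correct where it is used, and when events are few each one needs the right grade.

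A reader might infer that the protocol contradicts itself, because entry and stopping act on one domain while grading needs two. The documents do not support that. The entry and stopping rules are action thresholds for an individual baby, and the stopping rule asks only for consideration at the clinician's discretion. A sensitive action threshold can sit beside a stricter outcome grade. Nor would the proposed fix align the two. Of the 98 patterns with some domain above 2, 6 are now ungraded and 18 are Grade 1; after the fix 4 remain ungraded and 12 remain Grade 1. The 4 are isolated dryness or erythema.

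A reader might also infer that the trial would miss skin breakdown, or that emollient will look falsely safe. The first is wrong because the absolute score counts breakdown. The second would need rates and durations of dryness and breakdown that the protocol does not give.

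Finally, tables of breakdown by randomised factor are ordinary SAP content, and their absence from a brief protocol section is no fault. The definition of the grade is different: it is fixed in the protocol, and an SAP that applied it would inherit the problem.

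**Conclusion.** The point holds as a fault in the definition of the grade. As written, Appendix I returns the middle domain score. It understates breakdown in 30 of 125 possible patterns, by up to four levels, and leaves breakdown alone ungraded at any extent. A change in dryness alone can also move the grade. This follows from the text of Appendix I without any assumption about event rates.

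The reach is narrow: the graded secondary analysis of the safety co-primary, and the grade attached to a serious skin event. The primary absolute-score analysis, the comparison of SAE frequency by group and the protection of individual babies are not affected. The change is worthwhile and cheap, but the trial's main conclusion does not depend on it.

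**What to change.** Amend Appendix I so that the grade is the higher of (a) the grade under the current two-category rule and (b) the breakdown score. Breakdown over more than half the skin alone then becomes Grade 4, and (1, 0, 4) moves from Grade 1 to Grade 4. An option is to let (b) apply only from breakdown 2, which changes 29 patterns instead of 30.

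**Cost.** A sentence in Appendix I. The three domain scores are already recorded, so the amended grade can be derived for every assessment with no new data.

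**Downsides.** Without the threshold at 2, breakdown 1 alone (under 5% of skin) becomes Grade 1. Isolated dryness or erythema stays ungraded under either version.

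**Optional, in the SAP.** Tabulate any breakdown and the worst breakdown score per baby by randomised factor, so that the regimen choice can be read alongside the domain of most concern.
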